4.11.1.5 Interim Analyses

An interim Analysis has been introduced with Study Protocol, Version 7.0 (December 14, 2021). Purpose of the IA was to have an early look into selected efficacy results in an unblinded fashion. Safety results were not part of the IA.

The Conditional Power method was employed to assess study early futility or efficacy.

Based on the IA results, TREVI took decision not to proceed further with this proof of efficacy study. No sample size re assessment has been considered based on IA results.

IA unblinded results were not disclosed to the main blinded team (including Project Leader, Data Management, Biostatistician and Statistical Programmers).

IA unblinded results were visible only to:

- PAREXEL separate unblinded team (including unblinded Biostatistician and unblinded Statistical Programmers);
- TREVI designated unblinded representative.

Strategy to prevent unauthorized disclosure of unblinded information are detailed in the Blinding Maintenance Plan.

| Trevi Therapeutics, Inc. | |
|--------------------------|---------------------------|
| TR12 | Statistical Analysis Plan |
| | |

4.11.1.6 Examination of Subgroups

Primary endpoint summaries will be produced for gender and anti-fibrotic therapies (defined in section 4.9 of this SAP) subgroups.

As described in section 4.11.3, selected secondary endpoint summaries will be produced for gender and anti-fibrotic therapies subgroups.

4.11.2 Analysis of Primary Efficacy Variable

The primary variable for the assessment of efficacy is presented at section 3.2.1.1 of this SAP.

The primary analysis for the primary endpoint will be on the natural log scale of the daytime cough frequency data. The difference between NAL ER at 162 mg dose level and placebo will be estimated using a mixed-effects model with sequence, period and treatment as fixed effects, the log-transformed study baseline value as a covariate, , and subject as a random repeated effect.

While measurements taken at different time points are expected to correlate, measurements taken at adjacent time points are assumed to be more correlated than measurements further apart, and therefore the compound symmetry covariance structure will be used.

Sensitivity analysis will be conducted with other covariance structures to evaluate the robustness of the compound symmetry structure considered to model the within-subject errors. The following covariance structures will be utilized respectively:

- 1. Unstructured covariance
- 2. Heterogeneous Toeplitz
- 3. Autoregressive AR(1)

A simplified version will be implemented by excluding the site and gender adjustment. The change from study baseline in log-transformed scale (i.e., log-transformed daytime cough frequency at Day 22 – log-transformed study baseline) will be used as the dependent variable.

In the above defined statistical model, the sequence effect can be interpreted as the carry-over effect: hypothesis testing of sequence effect is equivalent to a test of carry-over effect; should sequence results as non-statistically significant, the sequence effect will be removed from the model, knowing that a carryover effect can be excluded.

There will be no imputation for dropouts or missing data for assessments not completed at study visits. In case of no cough registered in the daytime, in order to allow the log transformation 1 cough will be imputed for derivation of daytime cough frequency.

The following SAS code will be used as reference for the described analysis of primary efficacy endpoint:

```
proc mixed;
class SUBJ SEQ PERIOD TRT;
model log (cough Day 22/ baseline) = PERIOD TRT SEQ / cl alpha=0.05 est
solution;
random site / type=cs sub=SUBJ (SEQ);
estimate 'Day 22: Active - Placebo' trt 1 -1 / e cl;
<Add /modify "Ismeans" and "estimate" statements as needed preserving the
model>
run;
```

In the presentation of results, log-scale fitted means at Day 22 will be exponentiated back and percentage changes will be presented in table. A code similar to the below will be used:

```
geomean_perc_change=100*(exp(estimate)-1);
sdrerrback=((logStdErr**2)*((100*(exp(Estimate)))**2))**0.5;
geomean_perc_lowercl=geomean_perc_change-(quantile('NORMAL',
0.975)*sdrerrback);
geomean_perc_uppercl=geomean_perc_change+(quantile('NORMAL',
0.975)*sdrerrback);
```

Where SEQ is study Arm (i.e. Arm 1: NAL-ER + Placebo; Arm 2: Placebo + NAL-ER); Period corresponds to the Study Period; TRT is actual treatment received at the time of the assessment (i.e. NAL-ER; Placebo); SITE is the investigational site.

The above described primary analysis will be executed also on the FAS, as well the same analysis will be repeated on completers as a sensitivity analysis.

As an additional sensitivity analysis, a negative binomial model will be fitted with the number of coughs at Day 22 as the outcome, with terms for sequence, and treatment, as well as study baseline cough frequency, and duration of daytime (in hours) as an offset. Site will be a random effect with an unstructured covariance matrix.

Following SAS code will be used as reference for the described sensitivity analysis of primary efficacy endpoint:

```
proc glimmix;
class SEQ TRT PERIOD;
model COUGH = TRT BASE DAYTIME SEQ PERIOD dist=negbinomial solution e cl;
random intercept / subject=SITE type=un;
lsmeans TRT / e cl;
estimate 'Day 22: Active - Placebo' trt 1 -1 / e cl;
<Add /modify "lsmeans", "estimate" statements as needed preserving the model>
run;
```

Where SEQUENCE is study Arm (i.e. Arm 1: NAL-ER + Placebo; Arm 2: Placebo + NAL-ER); TRT is actual treatment received at the time of the assessment (i.e. NAL-ER; Placebo); COUGH is number of coughs at timepoint; BASE is the study baseline cough frequency; DAYTIME is duration of daytime (in hours).

A by subject listing will be provided for primary variable as defined in SAP section 4.2.4.

Daytime cough frequency will be summarized by actual treatment received in terms of absolute values and change from study baseline as defined in SAP section 4.2.5. A similar summary table will be produced for gender and anti-fibrotic therapies subgroups, including presentation of stratified means (SAS PROC SURVEYMEANS may be used).

Plots showing the absolute mean change from study baseline in daytime cough frequency by actual treatment received will be provided on both FAS and Completers analysis sets. Similar plots will also be presented by gender and anti-fibrotic therapies subgroups.

From statistical model for primary efficacy endpoint analysis, the geometric mean (GM) for the two treatment and the 95% confidence interval for the GMR and the p-value from the hypothesis test of no difference between the treatment will be presented.

| Trevi Therapeutics, Inc. TR12 | | | | | Statistical Analysis Dlan |
|----------------------------------|-------|------|-----|-----|---------------------------|
| 1K12 | | | | | Statistical Analysis Plan |
| T 1 | 1 1 0 | | 0.1 | 007 | 1 1 0.50/ |

From statistical model for sensitivity analysis of the primary efficacy end point, the 95% confidence interval for the difference between the treatments least squares mean and the p-value from the hypothesis test of no difference between the treatment will be presented.

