4.11.1.2 Adjustments for Covariates

The primary efficacy analysis will be adjusted for the following covariates:

- 1. Subject (random repeated effect)
- 2. Study baseline measure of primary efficacy variable
- 4.11.1.3 Handling of Dropouts or Missing Data

Missing or dropout data will not be imputed for the purpose of data analysis.

The Primary Efficacy Analysis will be performed on the FAS and on Completers Analysis Set as sensitivity analysis; there will not be imputation of primary or secondary efficacy endpoints eventually missing at a specific timepoint.

Rules to handle with AEs partial onset and dates will be detailed in section 4.11.1.

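### The reference SAS code in SAP 4.11.2 does not fit the primary and negative binomial models that the text describes, and as printed it cannot test the within-subject covariance structure

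*SAP*

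**What the plan says.** **Primary model, text.** SAP 4.11.2 lists sequence, period and treatment as fixed effects, then "the log-transformed study baseline value as a covariate, , and subject as a random repeated effect". SAP 4.11.1.2 names the same two adjustments: "Subject (random repeated effect") and "Study baseline measure of primary efficacy variable". SAP 4.11.1.1 adds that the primary model adjusts for site. SAP 4.11.2 continues: "A simplified version will be implemented by excluding the site and gender adjustment", and makes the change in log cough frequency the response. For the covariance it says: "Sensitivity analysis will be conducted with other covariance structures to evaluate the robustness of the compound symmetry structure". The alternatives are unstructured (UN), heterogeneous Toeplitz (TOEPH) and AR(1), and the stated target is the within-subject errors.

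**Primary model, code.** The CLASS statement is "class SUBJ SEQ PERIOD TRT". The MODEL statement is "model log (cough Day 22/ baseline) = PERIOD TRT SEQ". The only random term is "random site / type=cs sub=SUBJ (SEQ"). A note in the block lets programmers adapt LSMEANS and ESTIMATE but asks them to keep the model. SAP 4.11.3.1 and 4.11.3.2 reuse this model for 24-hour and nighttime cough.

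**Negative binomial sensitivity analysis.** The text in SAP 4.11.2 makes hours of daytime an offset and lists sequence, treatment and baseline, with site random. The code lists DAYTIME and PERIOD among the MODEL effects and has no OFFSET= option. Protocol 11.7 includes a subject term; the SAP text and code do not. SAP 4.15 reports only the recruitment stop and added exploratory analyses.

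**The concern.** A programmer who keeps the printed model fits something other than the described analysis. One who follows the text must rewrite MODEL and RANDOM and choose the details after the SAP is final. Either way the primary analysis is not fixed in advance.

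Three things are at stake. The covariance sensitivity analyses could be reported as agreeing perfectly when they never varied the structure in question. The primary SE could depend on how sites happen to be numbered. And the negative binomial analysis, meant as a check on the primary result, would differ from its description in ways that make agreement or disagreement hard to read.

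**Working it through.** **1. The plan's own power.** Inputs from Protocol 11.1: 44 completers, 40% reduction, CV 1.00, two-sided 5%. Reading the CV as within-subject on the original scale, SD = sqrt(ln(1 + 1.00²)) = 0.8326. SE = 0.8326 × sqrt(2/44) = 0.1775. Effect = ln 0.60 = -0.5108. Power = Φ(0.5108/0.1775 - 1.96) = Φ(0.918) = 82.1%, or 80.3% with a t distribution on 42 df. The stated figure of at least 80% is reproduced, and these inputs are used below.

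**2. Text against code, primary model.**

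| Element | Text | Code |
|---|---|---|
| Log baseline | covariate | only inside the log-ratio response |
| Subject | repeated effect | no REPEATED, no intercept |
| Site | adjusted for (4.11.1.1); excluded in the simplified version | unclassed slope within subject |
| Response | change, stated with the simplified version | change, yet SITE is kept |

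**3. What the RANDOM line implies.** For subject i at a site with numeric code s_i, the printed code gives V_i = σ²I + s_i²τ²J. Compound symmetry (CS) by subject gives V_i = σ²I + τ²J. In the printed form each subject has one random coefficient, so its covariance matrix is 1×1 and TYPE= has no structure to change. In one simulated data set with codes 1-15 and 44 completers:

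| Model | Structure | -2REML | Estimate | SE |
|---|---|---|---|---|
| Code | CS, UN, TOEPH, AR(1) | 254.5053 | -0.55429 | 0.17308 |
| Text | CS, AR(1) | 241.6931 | -0.55429 | 0.13586 |
| Text | UN, TOEPH | 239.1213 | -0.55429 | 0.13586 |

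The -2REML values of the two models are not comparable, because their fixed effects differ. What matters is one fit under the code and two under the text. Even correct code yields only two, because each subject has two records.

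**4. Size for the primary SE.** The estimate in completers comes from within-subject differences, and the study baseline is constant within a subject, so both models give the same estimate. The SE differs because between-subject variation that does not follow s_i² is pushed into σ². Assumptions: 3000 trials per setting, subjects spread evenly over 15 sites (Protocol synopsis: up to 15), within-subject SD 0.833, codes 1-15, REML, t with n - 2 df. The correlation of a subject's two changes is assumed.

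| Correlation | 0.3 | 0.5 | 0.7 |
|---|---|---|---|
| SE ratio, code / subject intercept | 1.09 | 1.18 | 1.28 |
| Power, code | 74.9% | 69.2% | 62.0% |
| Power, subject intercept | 80.7% | 80.0% | 81.1% |
| Type I error, code | 3.3% | 2.1% | 1.5% |
| Type I error, subject intercept | 4.8% | 5.0% | 4.8% |

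Both changes subtract the same baseline. With equal variances v and equal correlations r of the three log frequencies, their correlation is v(1-r) / [2v(1-r)] = 0.5, the middle column. A second simulation, with between-subject SD 0.4/0.8/1.2, gave ratios of 1.10/1.19/1.28 for codes 1-15. Both simulations gave 1.00 for codes 101-115.

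Recruitment stopped early (SAP 4.14, 4.15) and the final n is not given, but the ratio hardly depends on n: 1.09/1.17/1.27 with 36 completers and 1.09/1.16/1.25 with 24. In full analysis sets with added one-period subjects (44+8, 44+16, 30+6) it is 1.18 to 1.21 with codes 1-15 and 1.00 to 1.02 with codes 101-115; with codes 1-15 the estimate also moves, by an SD of 0.03 to 0.05 log units. Omitting the baseline covariate alone costs 0.3% to 2.0% in SE there and essentially nothing in completers.

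**5. Offset.** An offset fixes the coefficient of log hours at 1; the code estimates a free coefficient on hours. With an assumed 14-18 awake hours and no treatment effect on awake time, the mean SE is 0.166 (offset) and 0.167 (covariate). If treatment shifts awake time by an assumed 2 hours, it is 0.166 and 0.224, and the two log rate ratios differ by 0.147 on average.

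**6. Subject term.** Model SE / actual SD without it (random site in the model, no site effect in the data, 44 completers, lognormal rates, maximum likelihood, 300 trials per setting, about ±4%):

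| Within-subject SD | ρ = 0.3 | ρ = 0.5 | ρ = 0.7 |
|---|---|---|---|
| 0.4 | 1.10 | 1.08 | 1.15 |
| 0.6 | 1.00 | 1.06 | 1.10 |
| 0.833 | 0.86 | 0.98 | 0.98 |

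A control at SD 0.833 with zero subject correlation, where nothing is lost by omitting subject, already gives about 0.78 to 0.79.

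**The case against.** The code is offered as a reference, and its response is an expression that PROC MIXED would not accept as typed, so a programmer must edit it. That is fair, but the note invites changes only to LSMEANS and ESTIMATE, and the departures lie in CLASS, MODEL and RANDOM.

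SAP 4.11.2 defines SITE as the investigational site, so its absence from CLASS may be a slip. Each subject belongs to one site, so classing SITE would restore a common subject variance under CS and remove the SE loss. This stands. It would still give no effect shared by subjects of one site, and would not supply the baseline covariate.

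A reader might infer that the four covariance analyses must give one fit. The documents print no code for the alternatives, and their reference to within-subject errors points towards a REPEATED statement. The result holds only if TYPE= alone is changed on the printed line and SITE is numeric.

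A reader might also take 62-75% as the trial's power. No site codes are given; codes such as 101-115 do no harm to the completer analysis, and a character SITE would stop the step visibly. Nor is baseline wholly absent: it is in the response.

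Finally, the missing slash before the distribution option, and the doubled comma where site may once have stood, may be extraction losses. Neither is counted.

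**Conclusion.** The mismatch between text and code is certain and should be fixed. For the primary model the harm ranges from none to an SE about 1.28 times too large, depending on unstated site codes. In completers the error is conservative: same estimate, lower power, no excess of false positives. Stronger claims, such as a biased completer estimate or inflated type I error, are not supported. The figures rest on the assumed site codes and correlations and on reading the CV as within-subject.

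For the negative binomial analysis, the offset error is negligible if awake time does not differ by treatment and can be material if it does. Leaving out subject ignores the pairing and loses precision; the model SE is too large when subject correlation is high and within-subject variability low. A reader might blame the low SE ratios on the missing subject term as well. The control with zero correlation shows that they mostly reflect fitting a negative binomial model to lognormal rates. The undeclared departure from Protocol 11.7 stands whatever its size.

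**What to change.** **Primary.** Replace the model part with `class SUBJ SEQ PERIOD TRT; model y = PERIOD TRT SEQ LOGBASE; repeated PERIOD / subject=SUBJ(SEQ) type=cs;`. Vary TYPE= on the REPEATED statement and report only CS and UN, because with two periods CS equals AR(1) and UN equals TOEPH. Either remove SITE, or put it in CLASS with its own RANDOM statement, and reconcile 4.11.2 with 4.11.1.1. State whether the code is the version with or without site and gender. The same correction then carries to 24-hour and nighttime cough.

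**Negative binomial.** Put SUBJ and SITE in CLASS. Replace the DAYTIME covariate by `offset=LOGHRS`, with LOGHRS = log(DAYTIME), and say in the text that the offset is log hours. Add PERIOD to the text. Add `random intercept / subject=SUBJ(SEQ);`, or declare and justify in 4.15 why the protocol's subject term was dropped.

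**Cost.** A few lines of code and one or two sentences in 4.11.2 and 4.15; no new data.

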9.2.3 Blinding and Randomization of Study Treatments

Randomization will be performed via IVRS/IWRS. Upon confirmation of eligibility by the study site and completion of all scheduled procedures at the Baseline (Day -1) visit, subjects will be randomized in a 1:1 ratio to either NAL ER tablets or placebo tablets for Treatment Period 1. Subjects will take the converse study treatment during Treatment Period 2 (the second crossover period).

9.3 **Procedure for Breaking the Randomization Code**

Under normal circumstances, the blind will not be broken. In the event of a medical emergency, when management of a subject's condition requires knowledge of the treatment assignment, the blind may be broken via the IVRS/IWRS.

Reasons for unblinding will be documented in the eCRF. The date and the identity of the person responsible for breaking the blind must be also documented.

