4.2.5 Data Summaries

Subject disposition, Demographics, Medical History, Treatment Exposure and Treatment Compliance tables will be summarized by sequence (see definition in section 4.2.1).

In efficacy and safety tables (including concomitant medications), results will be summarized under the actual treatment received (NAL-ER or Placebo) independently whether the NAL-ER (and Placebo) was received in Treatment Period 1 or 2. In other words, summaries will be presented by treatment received.

In most instances, the baseline visit for Treatment Period 2 will occur on the same calendar day as the Follow-up Visit 6 for Treatment Period 1; in any case, Visit 6 results will be used as Follow-up for Treatment Period 1, while the baseline for the Treatment Period 2 will be the study baseline (taking into account baseline definition from section 4.2.3).

Continuous data will be summarized in terms of the number of subjects with non-missing values, mean, standard deviation (SD), median, minimum and maximum, unless otherwise stated.

The following rules will apply to all descriptive statistic displays, where 'd' denotes the decimal places in the original reported value:

- n (number of non-missing observations): 0 decimal places (d.p.)
- Mean: d + 1 d.p.
- SD: d + 2 d.p.
- Median: d + 1 d.p.
- Minimum: d
- Maximum: d
- Statistics in percentage: 1 d.p.
- Confidence Intervals (CIs): d + 1 d.p.
- A maximum of 3 decimal places will be displayed.

All CIs will be reported as 2-sided and will be assessed at α =0.05 significance level unless otherwise stated.

Categorical data will be summarized in terms of the number of subjects providing data at the relevant time point (n), frequency counts and percentages. The denominator for the proportion will be based on the number of subjects who provided non-missing responses to the categorical variable. Any planned collapsing of categories will be detailed in the SAP text and the data displays.

Percentages will be presented to one decimal place. Percentages will not be presented for zero counts. Percentages will be calculated using n as the denominator.

In general, for categorical variables showing multiple possible categories, these will be displayed following the within variable logic criteria; where such a logic criterium does not exist (example: gender, race, AE SOC, AE PT), categories will be displayed by overall descending frequencies.

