4.5.2 Full Analysis Set

The Full Analysis Set (FAS) will consist of all randomized subjects who have taken at least one dose of study medication and provided study baseline and at least one post-baseline primary efficacy variable assessment during the treatment period. The FAS will be used for the primary efficacy analyses.

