4.11 Efficacy Evaluation

All efficacy summaries and analyses will be based upon the FAS as defined in Section 4.5, unless otherwise specified.

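### The FAS efficacy analyses label each recording by treatment received instead of the treatment randomised for that period, and no as-randomised analysis is planned

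*SAP*

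**What the plan says.** Randomisation fixes the treatment in both periods. Protocol 9.2.3 has patients "randomized in a 1:1 ratio to either NAL ER tablets or placebo tablets for Treatment Period 1" and continues: "Subjects will take the converse study treatment during Treatment Period 2". Arm and period together therefore give every recording a planned treatment.

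The SAP does not use that label for efficacy:

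- **Primary model (4.11.2).** The sequence term is the arm: "Where SEQ is study Arm (i.e. Arm 1: NAL-ER + Placebo; Arm 2: Placebo + NAL-ER". The treatment term is different in kind: "TRT is actual treatment received at the time of the assessment". The negative binomial sensitivity model defines its treatment term in the same way.
- **Tables (4.2.5).** One sentence covers efficacy and safety: "results will be summarized under the actual treatment received (NAL-ER or Placebo").
- **Primary variable summary (4.11.2).** "Daytime cough frequency will be summarized by actual treatment received in terms of absolute values and change from study baseline". Most of the secondary summaries and plots in 4.11.3 follow the same rule.
- **Analysis set (4.11 and 4.5.2).** "All efficacy summaries and analyses will be based upon the FAS as defined in Section 4.5", and "The FAS will be used for the primary efficacy analyses". The FAS definition says who is included. It does not say that patients are analysed as randomised.

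The Completers and per-protocol repeats (4.5.3, 4.5.4) change who is included, not how treatment is labelled. Protocol 11.3.1 says only that summaries are by treatment group.

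**The concern.** A comparison on a full analysis set is protected against bias because each value is counted under the treatment that chance assigned. If the drug had no effect, a label fixed by randomisation would be unrelated to the outcome by construction. A label fixed by what was later dispensed or taken carries no such guarantee. Labelling by treatment received is normal for safety tables; the difficulty is that the same rule is written for the primary efficacy contrast.

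The SAP's revision history gives the adoption of the FAS as primary set as a reason for the May 2022 draft. Coding by treatment received works against that aim. No planned repeat would show the difference, because all of them inherit the same label.

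**Working it through.** **1. The plan's own figure, and whether the point touches it.** Inputs from Protocol 11.1: 44 completers, 40% reduction, CV 1.00, two-sided 5%, 26% dropout. I read the CV as within-patient on the original scale.

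- Log-scale SD = √ln(1 + 1.00²) = 0.8326
- Effect = −ln(0.60) = 0.5108
- Standard error = 0.8326 × √(2/44) = 0.1775
- Effect / standard error = 2.88
- Power = 82.1% (normal) or 80.3% (noncentral t, 42 df)
- Number to randomise = 44 / (1 − 0.26) = 59.5, so 60

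The stated power of at least 80% and the 60 patients are reproduced. Nothing in this calculation depends on how treatment is labelled, so the point does not change the sample size.

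**2. When the two labels differ.** Take a patient in Arm 2 (placebo, then NAL ER):

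| What happened | Randomised label, P1 / P2 | Label as received, P1 / P2 | Consequence |
|---|---|---|---|
| Correct cards | Placebo / NAL ER | Placebo / NAL ER | Identical |
| Correct cards, doses missed or stopped | Placebo / NAL ER | No rule moves P2 to Placebo | No change of column |
| Placebo card in both periods | Placebo / NAL ER | Placebo / Placebo | No within-patient contrast as received; can be in the FAS, not in Completers |
| Cards swapped | Placebo / NAL ER | NAL ER / Placebo | Contrast reversed relative to the randomised label; can be in the FAS and in Completers |

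Only the last two rows matter, and both need a wrong card. The third cannot occur among completers, because SAP 4.5.3 requires receipt of both treatments.

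**3. Illustration of size.** Assumptions, none from the documents except the 0.60 and the 44: 44 FAS patients with both Day 22 recordings, 22 per arm; true ratio 0.60; m patients in Arm 2 given placebo again in Period 2; errors unrelated to outcome. The as-randomised log effect is half the difference between the arms' mean period differences. In Arm 2 the mean effect shrinks to ln(0.60) × (22 − m)/22, so overall:

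as-randomised ratio = 0.60^(1 − m/44)

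| Wrong periods, m | As randomised | As received (simulated, 5,000 runs) |
|---|---|---|
| 0 | 0.60 | 0.60 |
| 1 | 0.60^(43/44) = 0.607 | 0.60 |
| 2 | 0.60^(42/44) = 0.614 | 0.60 |
| 4 | 0.60^(40/44) = 0.629 | 0.60 |

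The simulation gave 0.606, 0.615 and 0.628 for the as-randomised column, in agreement with the formula. With errors unrelated to outcome, the as-received ratio stays at the true value and the as-randomised ratio is diluted. The table therefore shows the cost of the fix. It does not show bias in the SAP's rule. Adding 1.0 log unit to the wrong-card recordings also left the as-received ratio at about 0.60 and moved the as-randomised ratio to 0.618, 0.645 and 0.686. That shift was added to one arm only, so it does not represent a prognostic difference that randomisation would have balanced.

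**The case against.** The strongest reply is that the SAP explains its own phrase. Section 4.2.5 goes on to say that results are pooled whichever period the treatment fell in, and 4.2.6 states the same rule for figures without the word actual. A crossover needs a per-period treatment variable because sequence alone does not identify it. The authors may have meant no more than that. This reading is plausible. If it is right, the fix only records their intention. As written, though, SEQ is the arm while TRT is treatment received, and a programmer would take the actual-treatment variable.

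Several stronger readings are tempting, and the documents do not support them:

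- **That stopping or restarting reclassifies a patient.** TRT has two levels, and no rule turns a NAL ER patient who stops into a placebo patient. Protocol 9.1 keeps a patient who restarts on the same blister card. Protocol Tables 1 and 2 schedule no cough recording at the premature discontinuation visit. An undefined label could arise at most for someone who stops around Days 21 to 22.
- **That the model fails.** A mixed model with sequence, period and treatment remains estimable with an off-pattern patient.
- **That one patient's share of the sample measures the bias.** It is a share of patients, not an effect on the estimate.
- **That the rule has been shown to bias the result.** The illustration above shows no such bias. Bias would need card errors related to outcome. Tablets of identical appearance and dispensing through IVRS/IWRS make that hard to argue.

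There is also partial handling. SAP 4.4.2 has deviations classified at a blinded review and results examined with and without data affected by major ones, and 4.5.4 defines a per-protocol set. These could show sensitivity to a mis-dispensed patient, but neither is an as-randomised analysis.

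**Conclusion.** The point holds as a matter of definition. The primary FAS contrast is specified by treatment received, and no planned efficacy analysis uses the randomised treatment for the period. A reader might infer that the primary result is therefore not protected by randomisation. That goes too far: with no wrong-treatment period the two analyses are identical, and the documents report none. What is missing is the guarantee that the contrast follows the allocation if a wrong card was dispensed.

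The expected numerical effect is small, and the stated power and sample size do not change. This rests on dispensing errors being rare, which the documents make likely but do not count. The correction is still worth making, because it is standard practice and nearly free.

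**What to change.** In SAP 4.2.5 and 4.11.2, state that for FAS and Completers efficacy analyses, including the negative binomial model, TRT is the randomised (planned) treatment for that period as given by SEQ and PERIOD. Keep treatment received for the safety tables and, if wanted, for the per-protocol repeat. Split the 4.2.5 sentence so that efficacy and safety no longer share one rule. Add a listing of every period in which planned and received treatment differ. Settle the wording before general unblinding, since SAP 4.11.1.5 records an unblinded interim look before this SAP version.

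The cost is one sentence in each section, one variable in the efficacy programs and one short listing. The downside is the slight dilution shown above if a patient was mis-dispensed. With no such patient, no result changes.
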